### **5.3 Laboratory procedures**

A blood sample (venous +/- capillary) is taken at inclusion. A volume of blood of a maximum of 14.5 ml (in children < 14 years) or 30.5 ml ( $\geq$ 14 years) is taken for to meet routine clinical and monitoring needs, study laboratory analyses and sample storage.

For children < 14 years, the maximum volume to ensure safe sampling will be calculated on the basis of age, weight and capillary haemoglobin. If less than the required is possible, priority will be given as follows:

1. clinical necessity and monitoring
2. primary study analyses
3. secondary and exploratory study analyses
4. sample storage

The following samples will be collected (subject to consent and site capacity)

1. Fingertip capillary blood test (participants < 14 years of age)
  - a. Hemoglobin (determination of maximum blood volume in children < 14 years): QuikRead Go®, CRP/hemoglobin cells or HemoCue® Hb 301
  - b. CRP (only on capillary blood if simultaneously with hemoglobin by QuikRead Go ®)
  - c. Preparation of a maximum of 5 dried bloodstains: for storage + for secondary research

For participants  $\geq$  14 years of age, capillary blood is taken after the blood test. venous.

2. Venous blood sampling: depending on the maximum volume that can be withdrawn, the following samples will be taken in order of priority

- a. 4 ml (2 ml if < 14.5 ml can be collected from children < 14 years) EDTA tube
    - According to clinical need: blood glucose
    - Malaria TDR: SD Bioline pan-LDH & pf-HRP2
    - Thick drop
    - Dengue TDR: SD Bioline Dengue Duo
    - White blood cells and differentiation: HemoCue® WBC/DIFF
    - CRP (if not yet performed on capillary blood) : QuickRead Go®, cuvettes CRP/Hemoglobin (with Hemoglobin) or RDT

Centrifuge the remaining volume for aliquoting (into 2-5 aliquots of 350  $\mu$ L of plasma) and stored in the biobank at -80°. The aliquots will be partly used for metagenomic analyses, the remaining volume (if any) will be stored for secondary searches.

- b. Blood culture bottle (1-4 ml in children < 14 years, 20 ml in adults patients  $\geq$  14 years of age): according to routine monitoring criteria

- c. 2 ml serum tube: biochemical analysis according to clinical need
- d. 2 ml additional EDTA: storage and secondary research
- e. 2.5 ml PAXgene tube: storage in the biobank at -80°C, for research purposes.  
secondary (e.g. transcriptional profiling)

Blood cultures will be taken and analyzed in accordance with the monitoring protocol.  
(protocol approved in DRC and Belgium; IRB IMT 613/08, UZA CE 8/20/96).

Study analyses (except metagenomic analyses) will be performed at the IME and the HGK study laboratory. Samples for metagenomic analysis will be transported to the ITM laboratory in Antwerp (as agreed in a 'Material Transfer Agreement' - MTA). Local empowerment of partner institutions is planned as part of a second time.

Samples for secondary research will be stored in the biobank at the following sites or at the ITM, Antwerp. All relevant sample data will be recorded in the biobank database. Samples obtained and stored in the biobank belong to the research site.

The sponsor guarantees that an MTA will be drawn up and signed for each sample transfer in outside the research site. The intellectual property of the results belongs to the institution which receives samples. An agreement will be reached between the study sponsor and the institutions partners (INRB, CRSK or IME) prior to any secondary research, as well as the approval of the relevant ethics committees. No data will be shared before signature a data-sharing agreement.

The study will ensure that all laboratory activities, including transport, processing and storage, are carried out in compliance with the applicable standards, analysis, reporting of results and storage of samples, will be carried out in accordance with to GCLP. The laboratory will perform diagnostic tests in accordance with the following procedures and EN-ISO 15189 standards. A laboratory analytical plan will be created before the start of the study, describing all aspects in accordance with the WHO GCLP.

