## **9.5 Risks and benefits**

A venous +/- capillary blood sample is part of the study procedures, but is in any case also necessary in the clinical management of most patients. The 2 samples will be integrated. Sampling can be uncomfortable, even painful. Visit risk of complications from blood sampling is very low (may include haemorrhage in elderly patients), people with coagulation disorders, puncture site infection or thrombosis (superficial veins). The amount of blood to be collected for this study, both for routine and additional analyses, in no case exceeds the maximum of what is considered acceptable as safe for the patient. In any case, routine analyses for management will always be priority, if sufficient volume cannot be achieved. The greatest risk for participants is a potential breach of confidentiality of data, for which all measures will be put in place to limit them as much as possible. Apart from access to laboratory analyses that can improve management (some research biomarkers), there are no advantages to participating in the study. Compensation is still provided for a requested trip, this compensation does not exceed the usual burden of effort.

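### For children under 14 with a restricted blood volume, Protocol 5.3 gives two priority orders that disagree, and the tube order can let a mixed clinical-research tube displace clinically indicated ones

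*Protocol*

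**What the plan says.** Protocol 5.3 and the Synopsis rows on follow-up and laboratory analyses cover the same ground.

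- **Limit.** The total is capped at a "maximum of 14.5 ml (in children < 14 years) or 30.5 ml" from 14 years. For younger children "the maximum volume to ensure safe sampling will be calculated on the basis of age, weight and capillary haemoglobin". No formula or table is given.
- **Order by purpose.** When the full amount cannot be drawn, the list runs from "1. clinical necessity and monitoring" through primary analyses, then secondary and exploratory analyses, to "4. sample storage".
- **Order by tube.** For the venous draw, "depending on the maximum volume that can be withdrawn, the following samples will be taken in order of priority". The tubes are a (EDTA, 4 ml, or 2 ml in a child who cannot give 14.5 ml), b (blood culture, 1-4 ml under 14 years), c (serum, 2 ml, for biochemistry when indicated), d (extra EDTA, 2 ml, storage) and e (PAXgene, 2.5 ml, storage).
- **Content of tube a.** Glucose when indicated, malaria rapid test, thick drop, dengue rapid test, white cells with differential, and CRP if not already measured on capillary blood. What remains is spun into 2-5 plasma aliquots for metagenomics and the biobank.
- **Capillary step.** Under 14 years it is listed before the venous draw and includes "Preparation of a maximum of 5 dried bloodstains: for storage + for secondary research". From 14 years it follows the venous draw.
- **Commitment on protection.** Section 9.5 states that "routine analyses for management will always be priority, if sufficient volume cannot be achieved".

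**The concern.** Both lists claim to decide what happens when blood is short. The tube list is not merely a default for the full draw: it is conditional on the attainable volume, and its first entry contains the reduced 2 ml amount. A site that fills a to e in order takes exploratory and stored material, inside tube a, ahead of two tubes that serve care or surveillance. A site that follows the order by purpose cannot treat tube a as one unit at all.

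The dengue test shows the tension most clearly. Section 9.6 excepts its result from those passed to the care team, whereas 5.1 has blood culture results going directly to clinicians. Yet the dengue test sits in the tube ranked ahead of the culture.

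Two things are at stake. The first is a written assurance about small or anaemic children. The second is comparability. SAP 3.4 reports the number cultured and the proportion positive, SAP 4.3 lists positive blood culture, haemoglobin and age as candidate predictors, and SAP 4.5 presents results by site and age stratum. If volume limits removed cultures, the missingness would be tied to age and haemoglobin, and it could differ between sites that read the text differently.

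**Working it through.** **Inputs (Protocol 5.3).** Tube a 4 ml, reduced to 2 ml; b 1-4 ml under 14 years and 20 ml from 14 years; c 2 ml; d 2 ml; e 2.5 ml.

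**Reproducing the stated maxima.**
- Under 14 years: 4 + 4 + 2 + 2 + 2.5 = 14.5 ml.
- From 14 years: 4 + 20 + 2 + 2 + 2.5 = 30.5 ml.

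Both match, so the maxima are the sum of the venous tubes.

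**Volume at which a, b and c all fit, with a at 2 ml.**
- 1 ml culture: 2 + 1 + 2 = 5 ml.
- 4 ml culture: 2 + 4 + 2 = 8 ml.

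**Filling in the stated order with the culture at its 1 ml minimum.** Assumption: a tube is taken only if its full volume fits, and filling stops at the first tube that does not.

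| Safe limit | a | b | c | d |
|---|---|---|---|---|
| 2 ml | 2 | 0 | 0 | 0 |
| 3 ml | 2 | 1 | 0 | 0 |
| 4 ml | 2 | 1 | 0 | 0 |
| 5 ml | 2 | 1 | 2 | 0 |
| 7 ml | 2 | 1 | 2 | 2 |

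The culture first fits at 2 + 1 = 3 ml and the serum tube at 5 ml. Tube d is reached only at 5 + 2 = 7 ml, after b and c are complete. The dedicated storage tubes therefore never displace a clinical tube; any displacement comes from tube a.

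**Comparison with the order by purpose.** Tubes b and c alone need 1 + 2 = 3 ml at the culture minimum. Between 3 and 5 ml the outcome for c therefore depends on how much of tube a is treated as clinical. The documents give no volume for the individual tests in tube a, so that share cannot be computed.

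**Capillary spots.** The list by purpose ranks storage last, yet the spots are listed before any venous tube in children under 14. No spot volume is given, and no text says where they rank against the venous tubes.

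**The case against.** The best defence is that the tube order largely implements the order by purpose. Tube a carries glucose and malaria tests as well as the primary biomarkers. It is already halved when volume is short, its plasma is only what testing leaves over, and d and e come last. Tubes b and c are themselves conditional on surveillance criteria or clinical indication. The list by purpose and section 9.5 can reasonably be read as overriding the tube list. The laboratory analytical plan, the procedures manual or the separate blood culture protocol may already hold an allocation rule. All of this narrows the point. It does not remove the contradiction, because the protocol calls both lists priority orders for a limited volume and never subordinates one to the other.

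Several stronger readings are tempting but unsupported:

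- **Research blood is simply drawn before clinical blood.** Tube a is mixed, and the pure storage tubes follow b and c.
- **The serum tube is lost even at 6 ml.** That happens only if the culture is filled to 4 ml, which is one clinical or monitoring tube competing with another; 2 + 2 + 2 = 6 ml fits all three.
- **About half of tube a is reserved for research.** Two aliquots of 330-350 µL are 0.66-0.70 ml of plasma. Converting that to whole blood needs a haematocrit the documents do not give, and nothing says that the minimum yield must be met in a restricted child.
- **Capillary blood breaks the stated maximum.** The Synopsis describes the maximum as venous, and the tube sum agrees. The finger-prick also has to come first in these children because its haemoglobin sets the limit, although that does not settle where the storage spots rank.

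**Conclusion.** The contradiction is in the text and bears on a stated patient-protection rule. Taken literally, the tube order can displace an indicated serum tube when the safe limit is below 5 ml, and the culture as well at about 2 ml (strictly, from 2 ml to just under 3 ml). Between 5 and 8 ml, whether all three fit depends on the culture volume chosen.

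This rests on tube a being taken at its full 2 ml, tubes being filled whole and in order, and the culture and biochemistry both being indicated. How many children fall in that range cannot be computed, because the rule linking age, weight and haemoglobin to volume is not given.

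A reader might infer that bacteraemia is under-detected in anaemic children, or that the sites will differ. The documents show neither. Both are possibilities if sites follow the tube list, and bacteraemia frequency is an exploratory endpoint.

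**What to change.** Reconcile the Synopsis rows on follow-up and laboratory analyses, section 5.3 and section 9.5 into one allocation table by available volume. The table should:

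- state which list governs;
- rank the clinical and primary part of tube a separately from its research and storage plasma;
- place the capillary dried spots in the same ranking.

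Use the same table at both sites and record the ml obtained per tube, so that missing or small cultures can be described against age and haemoglobin. The sponsor's clinicians decide the order; none is proposed here. The same edit can align the aliquot size, which is 330 µL in the Synopsis and 350 µL in 5.3.

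The cost is wording in the protocol and laboratory documents, a recording field per tube and brief retraining. Depending on the order chosen, some small children may contribute fewer stored aliquots.

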## 6. STATISTICAL METHODS

A detailed statistical analysis plan will be drawn up before recruitment begins. The analysis plan will provide a full description of the variables of interest, statistical methods (including the management of missing data, statistical adjustment, management of confounding factors and interactions), subgroup definitions and sensitivity analyses.

### 6.1 Variables of interest

- Demographic characteristics
- Basic clinical data (previous treatment, history, symptoms, clinical examination)
- Diagnostic hypothesis
- Patient outcome
- Examinations and treatments prescribed and carried out
- Outcome (survival with symptom resolution, survival without symptom resolution, death)

- Results of inflammatory biomarker analyses: CRP, white blood cells, and differentiation
- Results of etiological analyses: malaria, blood cultures, and germ antibiograms identified, metagenomic analysis, dengue TDR

### 6.2.1 Subgroup analyses

As this is a stratified study, all analyses will be presented by stratum (combination of strata). site and age group).

### 6.2.2 Multiplicity and missing data

An analysis of all available cases will be the main analysis for all objectives. The data data points, with the exception of clinical status, will be reported, and in In the case of limited missing data, multiple imputation will be used to recover the data. A subsequent analysis with the full set of imputed data will be carried out and compared with primary analysis. No adjustment for multiplicity is required in the analyses.

## 6.3 Sample size and power

Taking into account the main and strategic aims of this study (to describe the presentations and issues on the 2 sites, initiate the research capacity of the teams, provide the bases epidemiological studies), the expected sample size is based on the budget, reality and logistical feasibility. Size refers to the number of participants recruited in the laboratory phase of the study (following amendment 1 of the protocol). We plan to include 500 children at HGK / Mama Yemo, and 500 at HGR-IME + health centers in Kimpese. children + 500 adults for a one-year study period. This number is sufficient to provide data relevant to the study's objectives, and will also enable teams to manage study requirements. With an expected drop-out rate of 20%, we hope to have an accuracy of at least less  $\pm$  4.9% in each stratum (combination of site and age group) in the estimation of the proportion of the primary result.

## 7. QUALITY CONTROL AND ASSURANCE

The study will be conducted and monitored in accordance with this protocol and the applicable regulations.

for clinical research, in particular ICH-GCP and WHO-GCLP, and the procedures manual

~~TMOR~~Investigator ~~TMOR~~nator and the local principal investigators will coordinate all ~~study follow-up~~ activities, including :

- Develop and monitor workflows, schedules, milestones and performance measurement tools. progress.
- Hold regular team meetings to discuss project progress, activities and to resolve any problems that may arise. These can be face-to-face meetings or remotely, depending on distance.
- Ensure data quality and query resolution.
- Visit each clinical site regularly to :
  - check compliance with study protocol and procedures
  - verify that informed consents are valid
  - verify the source data by comparing it with data stored in the database
  - verify that confidentiality is fully respected. Monitoring standards require full verification of the presence of informed consent and the compliance with eligibility criteria.
  - Verify/monitor the quality of laboratory tests carried out according to GCLP practices and SOPs

The PI and the research staff at the site concerned will devote the necessary time and resources to this project.

to these monitoring activities. The investigator will also ensure that the insurance monitors of the sponsor (ITM CTU), the CRC (INRB) and the CRSK have access to all the documents and facilities related to the above-mentioned study and has the necessary space and resources to monitor and verify source data. The promoter will contact investigators concerned as soon as it is informed of an ongoing study center inspection by a regulatory authority or funder. Similarly, the investigator will inform the sponsor of any ongoing inspections. Monitoring of the study will be carried out by the CTU monitor and will be done by according to the monitoring plan.

## **8. DATA MANAGEMENT**

Data management procedures will comply with the ITM.

At each participating clinical site and each coordinating center, the investigator will keep a record of all the data collected.

hard copy of the main study file (IF: Investigator File), containing all the elements of the study (protocol, CRF, MOP) and regulatory requirements (ethics committee approvals), task delegation descriptions), CVs, memorandums of understanding).

Data management will be organized and carried out by the ITM/CTU data manager in collaboration with the INRB/CRC team and the CRSK. Full details of the treatment of study data will be described in the "data management plan", which will comply with SOPs and regulatory requirements. The study data will take into account the following essential elements.

### **Data collection**

Only data defined by the study protocol will be collected. Data collected will be registered via electronic forms (eCRF) in the study database at using a REDCap platform.

REDCap is a data capture and management software for clinical studies. REDCap complies with ICH quality standards and good clinical practice, as well as the recommendations and requirements such as CFR 21, Part 11 (e.g. electronic signature, audit trail, etc.). electronic). The software includes, among other things, an integrated system for tracking and managing queries, as well as data import and export functions in a variety of formats. shapes.

The eCRF and database have been designed in accordance with the specifications drawn up in the FIKI study. The specifications include the forms, the list of included variables in forms, programmed checks on eCRF to validate data at the time of data entry and automated queries to verify data and quickly identify or inconsistent. A complete validation of the eCRF system will be carried out, by in particular the input controls. It is only after final approval of the test phase and the validation report that data entry can begin.

Data capture and further processing will be carried out at all sites by our own staff under the responsibility of the site's principal investigator. Participants will be identified by study-specific participant code on the CRF and in the database (pseudonymization). The name and any other identifying details will be kept only on the recruitment site and will not be disclosed to third parties.

~~Will NOT be included the REDCap platform and database. ITM will have access at all times to access to a database export for follow-up activities.~~

### **Confidentiality and security of participant data**

Study participants' personal information will be treated confidentially.

Information such as the participant's name or any other data likely to make it possible to identification will not be recorded in the study database, nor in the database of the no other paper documents or electronic files used for the study. Each patient will receive a unique study code that will be used for registration in the study database. The

the name and contact details of each participant and the link to the unique study code will be retained and access to them will be restricted to clinical site personnel.

Access to paper documents and electronic files required for data management will be provided by strictly limited to ITM-authorized study personnel. Study computers and files

eCRF will only be accessible with a personal username and password. A list of of authorized users of eCRFs (and the database) will be kept at ITM and updated as required. study.

A data backup will be performed at server, computer and/or database level. data.

### **Data quality and verification**

Best practices in CRF design, such as the use of codes and checkboxes, and drop-down menus, will improve data quality. A system will be set up for data entry, verification, query resolution, backup and, last but not least, database locking. In addition to automatic verification checks will also be carried out to identify out-of-spec data, data with a high and inconsistent data. The central data manager, the coordinating investigator, the INRB team and the sites, will hold regular teleconferences on data management throughout the study.

### **Record-keeping**

Electronic documents for data management purposes, including txt and pdf formats, the Excel files, REDCap databases and their extractions, eCRF-generated files (in study descriptions), programs and e-mails will be stored in a secure and organized in a specific access-controlled data management subfolder on the server of ITM. Paper documents used for data management, such as mail printouts, data lists and data management documentation will be stored at the ITM in special specific files. ITM will ensure that access to these paper and electronic files is controlled. (e.g. in closed cabinets or rooms). Details on shelf life paper documents and electronic files are available in the section Archiving (see below).

### **Data sharing**

Study data relating to participants will be available for sharing within a given timeframe. reasonable after the study and in accordance with the research data sharing principles of ITM.

The notion of "data sharing for secondary research" will also be indicated in the informed consent form.

The study's anonymized data will be supplemented by metadata and the documentation, such as the study protocol, annotated CRFs and other information such as codes that together form a dataset, but will not include any direct identifiers. The researchers can ask ITM to access anonymized data for specific research purposes. or secondary analyses via a controlled access procedure.

### **Training**

For the study to be optimally implemented, all the teams involved must have a good understanding of the subject.

knowledge of the study documents and tools, as well as good clinical practice, and principles of research ethics. Specific training will be given to all members of the study team involved in patient care, data collection and data entry data verification and data monitoring. All those involved in the study will be trained before inclusion begins. They will also receive ongoing training throughout the year throughout the study.

